## Research process and methods

Method; Select 30-45 subjects with unstable, restricted, or uncomfortable ankle joints as observation subjects, and randomly divide them into ankle joint blood flow restriction training combined with IASTM group (n=10-15), ankle joint blood flow restriction training alone (n=10-15), and traditional ankle strength training (n=10-15). The intervention lasted for 4-6 weeks, once a week. Cumberland ankle instability assessment, FAAM ankle function assessment score, and ankle range of motion measurement were performed at three time points before intervention, after the first intervention, and after 4 weeks/6 weeks of intervention for the three groups. The ankle strength test was only compared and analyzed at two time points before and after intervention.

Process: This study is divided into three stages: pre intervention stage, post initial intervention stage, and post intervention stage. In the pre intervention stage, researchers will conduct preliminary evaluations and data statistics on subjects, including Cumberland ankle instability assessment, FAAM ankle function assessment score, and ankle range of motion measurement. During the intervention phase, participants from each group will undergo a 6-week exercise intervention, with a training frequency of 2 sessions per week and each session lasting 20-30 minutes. During BFRT exercise, a cuff will be wrapped around the proximal one-third of the upper limb of the subject to improve muscle strength and endurance by restricting blood flow. In this state, corresponding ankle training movements (stability training, ankle peripheral muscle group training) will be completed.

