## Statistical analysis

This study used SPSS 26.0 statistical software for data reading, testing, and statistical analysis.

The general information of the subjects is analyzed using an independent sample t-test. The measurement data conforms to a normal distribution. Because there are three time points (pre intervention, first intervention, and 6-week intervention) in the experimental data for measuring ankle joint function indicators and range of motion indicators, repeated measures analysis of variance is used for data statistics and analysis. Ankle joint strength was only measured at two time points (before intervention and after 6 weeks of intervention), and the data was only analyzed using paired t-tests. P<0.05 is a significant difference with statistical significance.

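### No sphericity correction or covariance model is specified for the three-visit repeated measures ANOVA; uncorrected, its error rate could lie anywhere from 5% to about 8.6% (time) or 9.7% (group-by-time)

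*Combined protocol and SAP*

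**What the plan says.** The Research process and methods section plans three arms, 30-45 subjects in total and 10-15 per arm. CAIT, FAAM and ankle range of motion are measured "at three time points before intervention, after the first intervention, and after 4 weeks/6 weeks of intervention". The Statistical analysis section gives the number of visits as the reason for its method: "Because there are three time points (pre intervention, first intervention, and 6-week intervention) in the experimental data", and so "repeated measures analysis of variance is used for data statistics and analysis". The only decision rule is "P<0.05 is a significant difference with statistical significance". The software is named ("This study used SPSS 26.0 statistical software for data reading, testing, and statistical analysis"), but not the procedure or the line of output to be reported.

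Neither section mentions a test of sphericity, a Greenhouse-Geisser or Huynh-Feldt correction, a multivariate test or a covariance structure. Neither says whether the effect of interest is time or group-by-time. No SD, correlation or epsilon appears anywhere in the documents. Strength is measured at two visits only and goes to paired t-tests.

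**The concern.** The univariate F tests for time and group-by-time hold their level only if the differences between every pair of visits have the same variance (sphericity). If they do not, the nominal degrees of freedom are too large and the P values too small.

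This design is prone to that failure. The first two assessments are separated by a single session and the third follows weeks of training. CAIT asks about the frequency and impact of symptoms, which one session can hardly change, so its first two values may be close to each other and both may sit further from the last. This is an inference from the design, not something that the documents report.

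Every three-visit outcome is exposed: CAIT, FAAM-ADL, FAAM-SPORT and four movement directions. SPSS can produce corrected and uncorrected P values from the same data, and the plan does not say which one is compared with 0.05. That choice is left open until the results are known, and with 10-15 per arm a borderline result could turn on it.

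**Working it through.** **Inputs from the documents.** Nominal level 0.05; k = 3 visits; 3 arms; N = 30 (10 per arm) or N = 45 (15 per arm), equal allocation assumed. **Not in the documents, so assumed and varied:** the SDs and between-visit correlations. The plan gives no error-rate calculation of its own beyond the nominal 5%.

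**Step 1. Epsilon.** Assume equal SDs, correlation a between visits 1 and 2, and correlation b of each with visit 3. The two orthonormal contrasts among visits are then uncorrelated, with variances (in units of the common variance)

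L1 = 1 - a, L2 = 1 + a/3 - 4b/3,

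and epsilon = (L1 + L2)² / [2(L1² + L2²)]. With three visits the lower bound is 1/(k - 1) = 0.5.

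- a = 0.9, b = 0.6: L1 = 0.10, L2 = 0.50, epsilon = 0.36/0.52 = 0.69.
- a = 0.95, b = 0.5: L1 = 0.05, L2 = 0.65, epsilon = 0.49/0.85 = 0.58.
- a = b = 0.7: L1 = L2 = 0.30, epsilon = 1. The dates of the visits do not enter.

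**Step 2. Error rate of the uncorrected test (Box approximation).**

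- Time: P{F[2e, 2e(N-3)] > critical value of F[2, 2(N-3)]}.
- Group-by-time: P{F[4e, 2e(N-3)] > critical value of F[4, 2(N-3)]}.

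Here e is epsilon. For N = 30 the error degrees of freedom are 2 × 27 = 54 and the critical values are 3.168 (time) and 2.543 (group-by-time). For N = 45 they are 2 × 42 = 84, with 3.105 and 2.480.

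| Epsilon | Time, N=30 / N=45 | Group-by-time, N=30 / N=45 |
|---|---|---|
| 1.0 | 5.0 / 5.0% | 5.0 / 5.0% |
| 0.9 | 5.6 / 5.6% | 5.7 / 5.7% |
| 0.8 | 6.3 / 6.2% | 6.5 / 6.5% |
| 0.7 | 7.0 / 6.9% | 7.4 / 7.4% |
| 0.6 | 7.8 / 7.7% | 8.5 / 8.4% |
| 0.5 (bound) | 8.6 / 8.5% | 9.7 / 9.6% |

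At epsilon = 1 the nominal 5% is recovered, as it should be.

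**Step 3. Simulation under the null.** 200,000 trials per scenario, normal data, 10 and 15 per arm. Ranges cover both sizes; the last column covers both effects.

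| a; b | Epsilon | Time, uncorrected | Group-by-time, uncorrected | Greenhouse-Geisser |
|---|---|---|---|---|
| 0.7; 0.7 | 1.00 | 5.0% | 5.0% | 4.6-4.8% |
| 0.8; 0.7 | 0.94 | 5.2-5.3% | 5.3-5.4% | 4.6-4.8% |
| 0.8; 0.6 | 0.86 | 5.6-5.7% | 5.8-5.9% | 4.8-4.9% |
| 0.9; 0.8 | 0.86 | 5.6-5.7% | 5.9-6.0% | 4.8-4.9% |
| 0.9; 0.6 | 0.69 | 6.6-6.8% | 7.3-7.4% | 4.9-5.1% |
| 0.95; 0.5 | 0.58 | 7.7-7.8% | 8.6-8.7% | 5.0-5.1% |

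If instead correlation decays at 0.9 per week, a second visit at week 1 gives 6.9-7.0% (time) and 7.7% (group-by-time). A second visit almost at baseline gives 8.5-8.6% and 9.6-9.7%, close to the bound. Over all scenarios and runs, the corrected tests stayed within about 4.5-5.2%.

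**The case against.** A reader might infer that the visit schedule itself breaks sphericity and that the trial's error rate is therefore 7-9%. The documents do not support that.

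- **Spacing is not enough.** With equal variances and equal correlations the test stays at 5% however the visits are spaced. The 7-9% for group-by-time needs epsilon of roughly 0.55-0.70, and the documents give nothing that fixes it.
- **The first two visits need not be nearly identical.** The second follows an active session, which in the combined arm includes soft-tissue release meant to restore movement. Varying acute responses could lower the correlation for range of motion. Baseline CAIT is also capped at 24 by eligibility, while later values are not. With milder correlations the inflation is one percentage point or less.
- **The plan does not choose the uncorrected test.** A Greenhouse-Geisser analysis is still a repeated measures ANOVA; the text is silent.
- **Other sources of error are larger.** With at least seven outcomes at 0.05 and no primary outcome named, the chance of at least one false positive is 1 - 0.95^7 = 30% if they were independent, even under perfect sphericity.

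All four points stand, and they limit the size and certainty of the claim. They do not remove the gap. A plan silent on correction permits an anti-conservative test in a design prone to needing the correction, and leaves the choice of P value until the data are in. The multiplicity problem is separate and does not excuse this one.

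**Conclusion.** The concern holds in a limited form. The plan specifies no sphericity correction or covariance model for CAIT, FAAM and range of motion. If uncorrected P values were reported, the true error rate would lie between 5% and about 8.6% for time, and between 5% and about 9.7% for group-by-time. These upper limits follow from k = 3 and 10-15 per arm alone. Where in that range the trial falls depends on a covariance that the documents do not give: about 7-9% for group-by-time with correlations of 0.90-0.95 between the first two visits and 0.5-0.6 with the last, about 5-6% with milder ones. None of these is an established error rate for this trial.

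The between-group main effect and the two-visit strength comparisons are not affected. The last visit is at 4 or 6 weeks in Research process and methods and at 6 weeks in Statistical analysis. Those sections must be reconciled, but this does not change the result.

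**What to change.** Add to the Statistical analysis section that, for CAIT, FAAM and range of motion, Greenhouse-Geisser-corrected P values will be reported for time and group-by-time whatever a sphericity test shows. Alternatively, replace the ANOVA with a linear mixed model with unstructured covariance across visits and small-sample degrees of freedom. The error rates above were checked for the Greenhouse-Geisser option, not for the mixed model.

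A separate improvement, not needed to cure sphericity, is to name the between-arm contrast at the last visit, adjusted for baseline, as the main comparison. It uses data already planned, avoids the sphericity assumption, and held 4.8-5.2% in simulation.

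The cost is one or two sentences of analysis wording and, if sphericity does hold, a slightly more conservative test (4.6-4.8% instead of 5.0% in the equal-correlation scenario). No extra visits, subjects or measurements are needed.

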**Project Summary** 

Ethics Review Number of Wuhan Sports University School of Medicine:2023102

Chronic Ankle Instability (CAI) is a common sports injury disorder. Athletes also suffer from

patellofemoral pain in their daily lives and training. Instrument Assisted Soft Tissue Mobilization

(IASTM) is a physical therapy technique that uses specially designed tools such as metal or plastic

scraping boards to assist in handling soft tissue problems. Mainly used in rehabilitation medicine,

sports medicine, and plastic surgery, it is used to handle tension, adhesion, pain, and motor

dysfunction of muscles, fascia, and tendons [25, 26, 27]. Blood Flow Restriction Training (BFRT)

is a special training technique aimed at limiting blood flow through the use of cuffs or elastic

bands on the limbs, in order to promote muscle growth and improve strength

Therefore, in order to further optimize the rehabilitation process of CAI, this study designed a

comprehensive rehabilitation training program that combines blood flow restriction training

(BFRT) with ankle balance training, ankle peripheral reinforcement training, and IASTM physical

release. BFRT was chosen because it has the adaptability to generate muscle strength at lower

loads, providing a relatively low-risk approach for rehabilitation. The combination of ankle

balance training and reinforcement training, as well as the physical release of IASTM, is expected

to play a synergistic role in promoting the rehabilitation process. By comparing conventional

balance training with pure BFRT training, this study aims to evaluate the effect of BFRT assisted

rehabilitation on ankle rehabilitation of sports dance athletes, providing new theoretical and

empirical support for the rehabilitation field. Through in-depth research, it is expected to provide

more effective and comprehensive rehabilitation plans for sports dance athletes, improve their

rehabilitation speed and effectiveness, and better safeguard their health and career.

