# **Research Objective**

Through experimental observation of exercise intervention (blood flow restriction training

combined with low load ankle muscle strength training and balance training) combined with instrument tool therapy (Instrument Soft Tissue Release Technique, IASTM), the intervention effect on ankle function, strength, and joint range of motion of sports dance athletes with ankle instability was observed.

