## **Control Group**

The control group of this study consisted of traditional ankle joint stability training and ankle joint peripheral muscle group strength training, with the same specific training plan as the experimental group

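### Ankle strength is analysed only by paired pre-post t-tests, so the three randomised arms are never compared on it and equal arms can look different

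*Combined protocol and SAP*

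**What the plan says.** The Research Objective section gives one objective with three outcome domains: "the intervention effect on ankle function, strength, and joint range of motion of sports dance athletes". The Project Summary makes the aim comparative, against conventional balance training and BFRT alone. Research process and methods randomises 30-45 subjects to three arms of 10-15 each.

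On strength, the same section states: "The ankle strength test was only compared and analyzed at two time points before and after intervention". The Statistical analysis section repeats the timing ("Ankle joint strength was only measured at two time points (before intervention and after 6 weeks of intervention") and then fixes the method: "and the data was only analyzed using paired t-tests". The other methods in that section are assigned elsewhere. Repeated-measures ANOVA is for function and range of motion, and the two-sample test is for baseline description: "The general information of the subjects is analyzed using an independent sample t-test". The significance rule is "P<0.05 is a significant difference with statistical significance", with no adjustment for multiple tests.

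The Ankle joint strength test section measures force in four directions. The Control Group section gives the controls stability and strength training "with the same specific training plan as the experimental group". Neither the English text nor the Chinese text on process and methods contains a between-arm test of strength.

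**The concern.** A paired t-test on two time points tests whether mean force changed. It is silent on whether BFRT or IASTM changed it more than traditional training did, which is the question randomisation was meant to answer. The controls also do strength training, so a gain is plausible there without any BFRT or IASTM effect. Familiarity with the dynamometer test could add to the gain in any arm. A paired test cannot separate either of these from a treatment effect.

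A reader given three within-arm p-values will tend to compare them, and a significant result in one arm beside a non-significant one in another is not evidence that the arms differ. At stake is whether one of the three named outcome domains gets any randomised comparison, although the data for one are collected.

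A lesser mismatch of the same kind is that an independent-sample t-test handles two groups, and this trial has three.

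**Working it through.** The plan gives no sample-size calculation, effect size or standard deviation for strength, so there is no figure of its own to reproduce. The check asks how often three truly equal arms would give conflicting paired-t verdicts.

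**Inputs from the documents**
- Three arms, n = 10 to 15 each (Research process and methods).
- Paired t-test, significance at 0.05 (Statistical analysis). Sidedness is not stated; two-sided is assumed.
- Four strength directions (Ankle joint strength test).

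**Assumed:** the standardised pre-post change dz (mean change divided by SD of change) is the same in every arm. It is shown over the range 0 to 1.5.

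**Step 1. Power in one arm.** p is the probability that a noncentral t variable, with n − 1 degrees of freedom and noncentrality dz × √n, exceeds the two-sided 0.05 critical value in absolute size. For n = 10 and dz = 0.5 the noncentrality is 0.5 × √10 = 1.58 and p = 0.293.

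**Step 2. Mixed verdicts over three equal, independent arms** (at least one significant and at least one not): 1 − p³ − (1 − p)³. With p = 0.293 this is 1 − 0.025 − 0.353 = 0.622.

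| dz | p, n = 10 | mixed, n = 10 | p, n = 15 | mixed, n = 15 |
|---|---|---|---|---|
| 0 | 0.050 | 14% | 0.050 | 14% |
| 0.5 | 0.293 | 62% | 0.438 | 74% |
| 0.7 | 0.506 | 75% | 0.713 | 61% |
| 0.8 | 0.616 | 71% | 0.821 | 44% |
| 1.0 | 0.803 | 47% | 0.949 | 14% |
| 1.2 | 0.920 | 22% | 0.991 | 3% |
| 1.5 | 0.987 | 4% | 1.000 | 0.1% |

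The maximum is 1 − 0.125 − 0.125 = 75%, reached when p = 0.5 (dz about 0.7 at n = 10 and about 0.55 at n = 15). Simulation of 100,000 trials per scenario at dz 0, 0.5, 0.8 and 1.0 agreed to within half a percentage point.

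**Step 3. Large common change.** At dz = 1.0 and n = 15 all three arms are significant with probability 0.949³ = 0.855, about 86%. The arms then look alike, but a report of the BFRT arms' results alone would suggest a benefit when the between-arm effect is zero.

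**Step 4. Four directions.** The chance of a mixed pattern in at least one direction is no smaller than the single-direction figure. How much larger it is depends on the correlation between directions, which the documents do not give.

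**Step 5. A valid comparison.** One-way ANOVA on the change scores, simulated under the same equal-arm conditions, rejects 4.9-5.1% of the time whatever the common change.

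**Step 6. Precision of a between-arm comparison.** For a pairwise difference in change, with 80% power at two-sided 0.05, the detectable difference is 1.32 SD of change at n = 10 and 1.06 SD at n = 15. With Bonferroni over the three pairs it is 1.57 and 1.25 SD.

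**The case against.** The strongest reply concerns size. dz is not in the documents, and the range 0.5 to 0.8 straddles the point where mixed verdicts are most common. Over the whole range the rate runs from about 0 to 75%. If every arm gains a great deal, nearly every arm will be significant and the arms will look the same. That stands: the claim that equal arms look different is conditional on dz.

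The plan also never says that verdicts will be compared across arms. True, but it specifies no other way of comparing strength between arms.

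Some of the supporting text is weaker than it first appears. The Control Group section likens the controls' training to that of the experimental group and does not mention the BFRT-alone arm. The sentence in Research process and methods limits time points and does not by itself exclude an arm comparison. The method therefore rests on one sentence in Statistical analysis. That sentence is explicit, and nothing else in the documents supplies the missing comparison. It also does not say that the paired tests are run arm by arm; that is inferred, but pooling the arms would not compare them either.

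Finally, 10-15 per arm can detect only large differences, so a correct analysis may well be inconclusive. That is a reason to report confidence intervals, not a reason to leave the comparison out. The baseline t-test is a minor matter and adds little weight.

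**Conclusion.** The concern holds. A three-arm randomised trial that names strength among its outcomes prescribes no between-arm analysis of it, and the prescribed method cannot provide one. This does not depend on any assumed effect size.

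The risk of a misleading pattern does. With equal true change in all arms, two-sided 0.05 and dz of 0.5 to 0.8, three equal arms give mixed verdicts on a given direction 62-75% of the time at n = 10 and 44-75% at n = 15, against about 5% for a proper between-arm test. Outside that range the figure is 14% at dz = 0 and close to zero at dz = 1.5. This should be corrected before strength results are interpreted.

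The plan also does not say whether the repeated-measures ANOVA for function and range of motion includes a group-by-time term. That is a separate question.

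**What to change.** Replace the strength sentence in Statistical analysis. For each of the four directions, fit an ANCOVA of the 6-week force on arm (three levels), with pre-intervention force as covariate. Report the adjusted pairwise arm differences with 95% confidence intervals and base conclusions on these. Keep the within-arm changes as description only.

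State a multiplicity rule. Four directions by three pairs is 12 contrasts, so either name one direction and contrast as the main one or adjust across the set. Acknowledge the limited precision shown above when interpreting a non-significant difference.

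Summarise baseline characteristics descriptively by arm instead of using a two-sample t-test.

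The cost is a few sentences of SAP text and one model per direction in the SPSS package already named. No new measurements or participants are needed.

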#### **Quality Assurance**

This experiment undergoes strict quality control, including inclusion criteria for experimental subjects, setting of research indicators, assurance during the experimental process, management and analysis of data records after the experiment, all of which are guaranteed by the experimental leader! Quality monitoring is carried out during the research process, and any issues that arise are promptly adjusted and corrected to ensure the normal progress of the study. The implementation of quality assurance measures can improve the reliability and validity of research, making the results more credible, reliable, and scientific.

## **Expected results of the study**

This study is only a rehabilitation plan designed to improve the stability of athletes' ankle joints through physical therapy combined with exercise intervention. It is hoped that this experiment can provide rehabilitation ideas and methods for solving ankle joint function problems in athletes.

#### Achievement dissemination and publishing policies

Researchers will serve as the lead publisher responsible for the publication of this experiment and paper.

# **Project Deadline**

20/10/2023

Recruitment end date

19/011/2023

Overall test start date

20/11/2023

Overall Trial End Date 30/12/2023

## **Ethics**

The intervention of human ankle joint stability involved in this experiment involves physical therapy with external tools, without involving the use of any new drugs or rigorous ethical issues. When incorporating participants, they will be required to sign an informed consent form and submit an ethics review form to the school. Finally, it is confirmed that the informed consent of all subjects and/or their legal guardians has been obtained, and it is confirmed that this experiment has been approved by the ethical review of the human body experiment at Wuhan Sports University. Confirm that all methods are carried out in accordance with relevant guidelines and regulations.

